## **Examining Changes in Microbiota over the Course of PTSD Treatment**

The overall goals of this project are to evaluate the use of 5-day intensively-delivered Cognitive Processing Therapy to treat PTSD and to determine the associations between the microbiome, salivary cytokines, and the presence of and recovery from PTSD. Specifically, this study is designed to 1) determine whether individual Cognitive Processing Therapy (CPT) delivered twice per day over 5 consecutive days (CPT-5) is tolerable, acceptable, and effective in reducing PTSD symptoms, 2) determine the microbial signatures associated with PTSD, 3) evaluate whether the abundance and composition of microbiota and salivary cytokine levels change over the course of PTSD treatment, and 4) examine whether changes in microbial signatures are associated with changes in cytokine levels.

### **Scientific Review:**

Cognitive Processing Therapy (CPT) is an evidence-based psychotherapy for posttraumatic stress disorder (PTSD; Resick, Monson, & Chard, 2016) that has demonstrated efficacy and effectiveness in a large range of settings and a variety of populations (Monson et al., 2006; Resick et al., 2017; Resick, Nishith, Weaver, Astin, & Feuer, 2002; Resick, Williams, Suvak, Monson, & Gradus, 2012). Clinical outcome data from the Road Home Program Intensive Outpatient Program (IOP), which offers CPT daily over the course of three weeks to treat veterans with PTSD, show that participation in the IOP produces large PTSD and depression symptom reductions. This suggests that patients are able to safely and effectively work on their trauma on a daily basis with CPT and that the daily delivery of CPT may also be acceptable and effective.

While existing evidence-based interventions for PTSD, such as CPT, have been shown to be effective for the treatment of the disorder, it has also been suggested that underlying biology may contribute to treatment refractory PTSD. The microbiome has received increased attention and been proposed as an important factor that impacts brain function and mental health through what is referred to as the gut-brain-axis (Carabotti et al., 2015; Collins et al., 2014; Heijtz et al., 2011). However, it has yet to be determined what role microbiota play in PTSD and whether the abundance of various microbiota changes over the course of evidence-based PTSD treatment.

The proposed project will address these questions by examining microbial signatures of individuals with PTSD to establish whether previously identified microbial signatures (cf. Hemmings et al., 2017) can be found in another sample and whether those signatures can be found in oral microbiota in addition to fecal microbiota. The project will also examine whether microbial signatures change over the course of PTSD treatment to determine whether symptom improvement and changes in inflammatory marker levels are associated with changes in microbiota.

### **Inclusion and Exclusion Criteria:**

#### ***Inclusion Criteria:***

Individuals are eligible for the current study if they:

1. Are 18 years or older
2. Are fluent in English
3. Have experienced a Criterion A traumatic event during their lifetime
4. Have a PTSD diagnosis verified by the Clinician Administered PTSD Scale for DSM-5
5. Are interested in receiving evidence-based treatment (CPT) for PTSD and able to attend 10 therapy sessions over the course of one week (5 days)
6. Are willing and interested to complete self-report measures and clinician-rated assessments at multiple time points over the course of the study

***Exclusion Criteria:***

Individuals are excluded from the current study if:

1. The traumatic event occurred in the past month
2. They are currently suicidal or homicidal
3. They have a history of psychosis or mania
4. They have not been on a stable dose of medication for at least one month
5. They made changes to the diet in the past month or are planning to make changes over the course of therapy
6. They have completed an evidence-based PTSD treatment in the past 3 months or are currently receiving an evidence-based PTSD treatment
7. They have mental retardation or significant cognitive impairment that would prevent them from engaging in CPT
8. They have a serious or unstable medical illness or instability for which hospitalization may be likely within the next year
9. They have an active substance use disorder (within the past 3 months)
10. They are involved with current legal actions related to the traumatic event that is anticipated to be targeted during treatment
11. They have a history (within the past year) or presence of an eating disorder
12. They are currently taking or have taken an antibiotic in the past 30 days
13. They are currently taking a corticosteroid
14. They have had part of the digestive tract removed or altered within the past year
15. They have had any surgery or procedure within the past 30 days that has required fasting for more than 12 hours or bowel preparation beforehand
16. They have a visual or auditory impairment that would prevent them from fully participating in study activities

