### **Measures:**

Self-report measures, clinician-rated assessments, a computerized task, and biological sample collection will be used during the study. The assessment schedule below details the different assessment time points for each measure. Measures may also be administered as needed at clinically relevant intervals.

Measure	Time Point										Optional Booster Sessions
	Intake	1 Week Interim	CPT-5 Day 1	Daily	CPT-5 Day 3	1 Week Post	2 Week Post	1 Month Follow-Up	3 Month Follow-Up		
Demographics Form	X										
Screening Questionnaire	X										
CAPS-5	X					X		X	X		
C-SSRS	X					X		X	X		
DIAMOND	X										
Ohio TBI Screen	X										
PCL-5	X			X		X	X	X	X	X	
PHQ-9	X			X		X	X	X	X	X	
GAD-7	X					X	X	X	X	X	
PTCI	X				X	X	X	X	X		
ADL	X										
AUDIT-C	X					X	X	X	X		
DAST-10	X						X				
CD-RISC-10	X					X	X	X	X		
PROMIS-SF-8	X					X	X	X	X		
PROMIS-SD-SF	X					X	X	X	X		
PROMIS-SRI-SF	X					X	X	X	X		
RAND-12+	X					X	X	X	X		
FFQ	X								X		
Diet Changes			X			X			X		
Emotional Stroop Test	X					X		X	X		
Oral-Derived Microbiota Samples+	X		X			X		X	X		
Salivary Cytokine Samples+	X		X			X		X	X		
Human DNA from Whole Saliva Samples+	X										
Fecal-Derived Microbiota Samples*	X		X			X		X	X		

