Biological sample collection will involve the collection of fecal- and oral-derived microbiota, salivary cytokines, and human DNA from whole saliva. Fecal samples will be collected by participants using a home collection kit. Participants will be provided instructions and all necessary equipment for sample collection and storage by a member of the study staff and will bring samples to their next treatment session. For participants completing telephone/video session, a home fecal sample collection kit as well as sample collection instructions, storage instructions and pre-paid return mailing information will be shipped to them. Salivary samples will be collected by study staff during study visits. Participants will be instructed to drink water prior to the session to ensure hydration and to rinse their mouth with water 10 minutes before the testing session with no other food or drink after. Participants will be instructed to refrain from the following activities prior to the saliva testing sessions: visiting the dentist within 48 hours, drinking alcohol and taking over-the-counter medications within 24 hours, drinking caffeine, smoking, and engaging in vigorous exercise within 2 hours, eating a major meal within 1 hour, and eating or drinking products with dairy, high levels of sugar, or high acidity within 20 minutes. Salivary cytokines and oral microbiota samples and human DNA from whole saliva will be collected by a member of the study staff during the study visit.

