**Compensation:**

	Intake	CPT Day 1	1- Week Post	2- Week Post	1- Month Post	3- Month Post	Total
Completion of Measures & Provision of Saliva Samples*	\$20	N/A	\$40	\$15	\$40	\$50	\$165
Provision of Optional Fecal Sample	\$10	\$ 10	\$10	N/A	\$10	\$10	\$50
Completion of Optional Semi-Structured Interview			\$15				\$15
Total Compensation Possible	\$30	\$10	\$65	\$15	\$50	\$60	\$230

\* Provision of saliva samples not available to participants who opt to participate via telephone/video.

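### Antibiotic and corticosteroid use is screened at entry, but no record of either is described at the four later biosample points, so exposed samples may go unidentified

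*Protocol*

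**What the plan says.** Two items in the protocol's Exclusion Criteria concern drugs that the point is about. Item 12 reads "They are currently taking or have taken an antibiotic in the past 30 days" and item 13 reads "They are currently taking a corticosteroid". Both apply to the person at entry.

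The schedule under Measures places fecal, oral-microbiota and salivary cytokine samples at Intake, CPT-5 Day 1, 1 Week Post, 1 Month and 3 Months. The Compensation table pays for fecal samples at the same five points (row "Provision of Optional Fecal Sample"). Telephone/video participants give no saliva, so for them the point concerns fecal samples alone.

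No row of the schedule records antibiotics, corticosteroids or medication in general after intake. The Screening Questionnaire is given at Intake only. The nearest repeated item is the Diet Changes form, at Day 1, 1 week and 3 months; nothing says that it covers drugs. The saliva instructions ask participants to avoid "drinking alcohol and taking over-the-counter medications within 24 hours", but they describe no record and name neither drug class.

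The SAP's Data analysis text covers symptom outcomes. It contains no microbiota or cytokine model and no rule for drug-exposed samples.

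**The concern.** Aims 3 and 4 rest on change over time in microbiota and cytokines, and on how the two changes relate, in one treated group. No control arm shows what incidental drug use does over the same months. The period from intake to the last sample exceeds three months, so an entry check with a 30-day look-back cannot speak for the later samples.

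If a participant takes an antibiotic or a corticosteroid between samples, the resulting shift is counted as change during therapy. Chart notes may catch some cases, but exposure dates not collected during the study cannot be reliably recovered later. Without them, the analyst cannot show that exposure was rare or that the result holds without the exposed samples.

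**Working it through.** **Count from the documents.** Biosample points: 5. After intake: 5 − 1 = 4. Antibiotic or corticosteroid records described at those four points: 0. The plan states no figure to reproduce here.

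**Chance that the issue arises at all (assumed rates).** If a share q of participants start either drug between intake and 3 months, and all 80 planned participants give samples, the expected number exposed is 80q and the chance of at least one is 1 − (1 − q)^80:

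- q = 2%: 1.6 expected, 80%
- q = 5%: 4 expected, 98%
- q = 10%: 8 expected, over 99.9%

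Samples are optional, so the real denominator is probably below 80.

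**Effect on a test of change (illustration for Aim 3 only).** Stand-in: two-sided 5% paired t-test, no true change, within-person change with SD 1. Each later sample is exposed with probability p, and exposure shifts the change by d SD. Inputs assumed: p = 1, 2, 3, 5, 10%; d = 0.5, 1, 1.5; n = 80 (planned enrolment) or 40 (because samples are optional). That gives 5 × 3 × 2 = 30 settings, each with 40,000 simulated datasets.

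False-positive rate (%) when all shifts go the same way, for d = 0.5 / 1 / 1.5:

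| Exposed | n = 80 | n = 40 |
|---|---|---|
| 1% | 5.0 / 5.0 / 5.1 | 5.1 / 5.0 / 5.2 |
| 2% | 5.1 / 5.6 / 5.6 | 5.0 / 4.9 / 5.1 |
| 3% | 5.1 / 5.7 / 6.6 | 5.0 / 5.4 / 5.7 |
| 5% | 5.4 / 7.1 / 9.5 | 5.2 / 6.1 / 7.2 |
| 10% | 7.2 / 13.4 / 22.3 | 5.9 / 9.0 / 12.4 |

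Twenty-five of the 30 are at 7.2% or less. The other five are 9.5, 13.4 and 22.3 (n = 80) and 9.0 and 12.4 (n = 40). A rerun with a new seed gave the same pattern within simulation error.

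The mechanism is simple. The spurious mean change is p × d, to be compared with a standard error of about 1/√n. At p = 10%, d = 1.5, n = 80 this is 0.15 against 0.112, or 1.3 standard errors. At p = 3%, d = 1 it is 0.03 against 0.112, or 0.27.

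**Shifts in both directions.** With a random sign for each exposed person, the rate is 4.7–5.3% in all 30 settings. Only noise is added: the standard error grows by the factor √(1 + p·d²), which is 1.004 at 3% and 0.5 SD and 1.107 at 10% and 1.5 SD.

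**Flagged samples left out.** The rate is 4.8–5.1%. This is partly true by construction: once exposed samples are gone, d drops out and a valid test is run on clean data. The standard error grows by 1/√(1 − p): 1.015 at 3%, 1.026 at 5%, 1.054 at 10%.

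**The case against.** **An unseen form may ask this.** The content of the Diet Changes form is not shown. Nor is that of the fecal kit material ("Participants will be provided instructions and all necessary equipment for sample collection and storage by a member of the study staff"). The Compensation table pays for an interview ("Completion of Optional Semi-Structured Interview") that has no row in the schedule, so the schedule may be incomplete. The protocol also says: "Measures may also be administered as needed at clinically relevant intervals". All of this stands as a limit: the documents show that no scheduled record is described, not that none exists. As-needed use does not close the gap, because it is unscheduled and does not mention medication.

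**Later exposed samples break no rule.** A reader might infer that such a sample fails the protocol's own criteria. The documents do not support that. Items 12 and 13 decide who enters; no washout is set for later samples. Using the 30-day window as a flag is a reasonable extension of the entry rule, and no more.

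**The diet comparison proves little.** A reader might infer an oversight because diet is followed after entry and drugs are not. But the diet criterion looks ahead by its own wording ("They made changes to the diet in the past month or are planning to make changes over the course of therapy"), and the drug criteria do not. The difference need not be an oversight.

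**The effect is mostly small.** This is correct on the numbers above, and n = 80 assumes that everyone gives every sample. At an assumed n = 20, the worst same-direction setting is 8.2%, and all settings with 5% or less exposed are at 5.9% or below. The t-test also does not represent Aim 4 or multi-taxon sequencing data.

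**Conclusion.** The point holds as a cheap improvement to data collection; no error or contradiction is shown. Two drug exposures important enough to exclude people at entry have no described record at the four later sample points, so exposed samples may go unidentified.

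Its size depends on assumptions that the documents cannot settle. Bias is negligible if use is rare or if shifts go both ways. It could be material (about 9–22% false positives in place of 5%) only at 10% exposure with same-direction shifts of at least 1 SD, or at 5% exposure with 1.5 SD and n = 80. Exposure may be lower at Day 1 and 1 week, which follow soon after the entry check.

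A reader might conclude that the Aim 3 and 4 results will be biased. The documents do not support that, since neither exposure nor effect is given. They support only that, without a record, the trial may be unable to tell which case applies. Confidence is medium because an existing form may already cover this.

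**What to change.** At CPT-5 Day 1, 1 week, 1 month and 3 months, ask two dated questions: antibiotic use since the last sample, and corticosteroid use since the last sample. If an existing form already asks this, name it in the schedule instead.

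Flag samples taken within 30 days of an antibiotic or during corticosteroid use. Keep the all-samples analysis. Wherever the biosample analysis is specified, prespecify beside it a sensitivity analysis of the Aim 3 and 4 results without flagged samples, and report how many were flagged, even if none.

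**Cost.** Two short questions at four existing sample points, with no new procedure or staff and no change to eligibility or treatment. Burden rises slightly and self-report may miss some use. In the sensitivity analysis only, the standard error is about 1.5% larger at 3% exposed (0.03 × 80 = 2.4, so about 2 of 80 samples) and 5.4% larger at 10% (8 of 80).

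**Limit.** Leaving out flagged samples removes the bias only if reporting is complete and drug use is unrelated to the change that would have occurred without it. An infection that prompts an antibiotic may itself affect cytokines, so the sensitivity analysis should be read beside the main one and not in its place.

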**Research Plan:**

**Study Population:**

Trauma-exposed individuals will be recruited from the Rush Department of Psychiatry, Department of Behavioral Sciences, the Rush newsletters, the Rush website, Road Home Program: Center for Veterans and their Families, other Rush clinics, and postings to Rush/Road Home Program social media pages and website. Local first responders will also be recruited. Recruitment flyers will be posted in waiting areas in the Rush Departments of Psychiatry and

Behavioral Sciences. Approximately 200 individuals will be screened, anticipating that 40% of those screening positive on the phone and expressing interest in the study will be eligible and willing to participate (~40% of 200 screened = 80 participants). We plan to enroll at least 80 trauma-exposed individuals who meet the diagnostic criteria for PTSD, as assessed by a gold standard clinician-administered PTSD assessment, for the single-arm, open-label trial.

### **Study Activities:**

#### ***Eligibility Phone Screening:***

Individuals who are interested in participating in the proposed study will call in response to study recruitment flyers or will be called by the study staff once they have been referred, and they will then be screened via phone by a member of the study staff to be examined for eligibility. Individuals who meet exclusion criteria or who choose not to participate will be referred for other treatment as indicated. Potentially eligible and interested individuals will be scheduled for an in-person intake session, which may be conducted in 1-2 sessions based on the participant's scheduling availability. Informed consent will be obtained and signed at the beginning of the in-person assessment, prior to the conduct of any study activities. Alternatively, potentially eligible and interested individuals may schedule a telephone/video intake session. All telephone/video sessions will be conducted via a HIPAA compliant platform. Individuals who schedule telephone/video intakes will be sent a link to an electronic version of the consent form via REDCap prior to the conduct of any study activities.

#### ***Intake Assessment:***

The intake assessment will be used to confirm the fit for the proposed project. Clinical interviewers with a minimum of a Master's degree in Psychology who are not providing the treatment will administer structured diagnostic interviews (e.g. CAPS and DIAMOND). Study staff will administer brief computerized assessments (e.g. Stroop task) and a full self-report assessment battery via Qualtrics. Participants will also be emailed a link to an internet-based dietary assessment. If participants consent to providing biosamples, study staff will also collect microbiota, salivary cytokine samples, and human DNA extracted from whole saliva.

Completion of the intake assessment may take up to 4 hours and may take place over 1-2 days, depending on the participant's availability. Telephone/video intake assessments will include the administration of a brief computerized assessment and the provision of fecal samples but will not include the provision of saliva samples. Study staff will securely email the full self-report assessment battery to telephone/video intake participants via Qualtrics. Study staff will also securely email participants a link to the brief computerized assessment. All intake assessments will be audio recorded to establish diagnostic reliability. Intake assessments may also be audio and/or video recorded for research purposes.

#### ***Intensive Week-Long Cognitive Processing Therapy (CPT):***

The eligible individuals will undergo a course of 1-week-long Cognitive Processing Therapy (CPT-5). CPT-5 will be delivered twice per day over the course of five business days (Monday through Friday; 10 sessions total) at approved study sites or via the HIPAA compliant platform.

Each 50 minute session will closely follow the CPT protocol and will be conducted by either [name], other doctoral-level psychologists, postdoctoral fellows, or other Master's level (or higher) clinicians who have received the official two-day CPT training and who are not involved in study assessments. All CPT sessions will be audio and/or video recorded and an independent fidelity rater with experience in the treatment will randomly select and review 20% of all therapy audio recordings to ensure that the intervention is provided with fidelity, which will be defined as 80% or more of the maximum possible score on the official CPT fidelity rating scales. CPT worksheets and homework assignments may be collected and copied for research purposes. Individuals with telephone/video sessions will have the option to complete electronic versions of CPT worksheets and to upload them to a secure folder accessible only by the individual and study staff.

Changes in PTSD severity and other relevant symptoms will be assessed before, during, and after the course of CPT using well-validated clinician-administered, self-report, and computerized assessments. Completion of assessments may take between 20 minutes for self-report measures and 90 minutes for combined self-report, computer-based, and clinician-administered assessments. Fecal- and oral-derived microbiota as well as salivary cytokines will also be assessed at various pre-treatment, post-treatment, and follow-up time points to determine whether the microbiome and cytokine levels change over the course of CPT. Participants will have the option to opt out of providing these biological samples and still receive CPT-5. Participants completing telephone/video sessions can provide optional fecal samples and will complete brief computerized assessments, but will not provide saliva samples.

### ***Booster Sessions:***

Following their completion of the course of CPT, participants will be given the option to schedule up to three in-person or telephone/video booster sessions of CPT with their study therapist. If a participant decides to use any booster sessions, they must be used by the date of the participant's 3-month follow-up visit. All booster sessions will be audio and/or video recorded. CPT worksheets and homework assignments may be collected and copied for research purposes. Participants will complete self-report measures at each booster session they choose to use.

### **Measures:**

Self-report measures, clinician-rated assessments, a computerized task, and biological sample collection will be used during the study. The assessment schedule below details the different assessment time points for each measure. Measures may also be administered as needed at clinically relevant intervals.

Measure	Time Point										Optional Booster Sessions
	Intake	1 Week Interim	CPT-5 Day 1	Daily	CPT-5 Day 3	1 Week Post	2 Week Post	1 Month Follow-Up	3 Month Follow-Up		
Demographics Form	X										
Screening Questionnaire	X										
CAPS-5	X					X		X	X		
C-SSRS	X					X		X	X		
DIAMOND	X										
Ohio TBI Screen	X										
PCL-5	X			X		X	X	X	X	X	
PHQ-9	X			X		X	X	X	X	X	
GAD-7	X					X	X	X	X	X	
PTCI	X				X	X	X	X	X		
ADL	X										
AUDIT-C	X					X	X	X	X		
DAST-10	X						X				
CD-RISC-10	X					X	X	X	X		
PROMIS-SF-8	X					X	X	X	X		
PROMIS-SD-SF	X					X	X	X	X		
PROMIS-SRI-SF	X					X	X	X	X		
RAND-12+	X					X	X	X	X		
FFQ	X								X		
Diet Changes			X			X			X		
Emotional Stroop Test	X					X		X	X		
Oral-Derived Microbiota Samples+	X		X			X		X	X		
Salivary Cytokine Samples+	X		X			X		X	X		
Human DNA from Whole Saliva Samples+	X										
Fecal-Derived Microbiota Samples*	X		X			X		X	X		

